6.1 Clinical Evaluations

Participants will be seen by a study team member at screening, and maraviroc start dates (day 0 for immediate start group, and day 56/week 8 for the delayed start group) for a review of health history.

Participants will also be seen by a study team member every weeks while taking maraviroc (day 0, week 1, week 2, week 3 week 4 for the immediate start group, and Day 56/week8, week 9, week 10, week 11, week 12 for the delayed start group) and every 4 weeks prior to starting, and after completing maraviroc (week 8 and week 12 for the immediate start group, and day 0, week 4, and week 16 for the delayed start group) for adverse event monitoring.

6.2 Laboratory Evaluations

Blood will be collected by standard blood drawing techniques. All laboratory assays will be done at University of Maryland Medical Center or at the IHV research lab facilities depending upon the assay. Stored samples will be processed and stored at the IHV research laboratories.

Screening: CBC with differential; creatinine and hepatic function tests including; albumin, alkaline phosphatase, aspartate aminotransferase (AST), alanine aminotransferase (ALT) will be collected or outside records showing eligibility will be used. Hepatitis serologies and viral loads will be completed if medically indicated.

Research Visits:

At the first study visit the following tests will be done:

- Baseline HCV VL
- Serum storage (10 ml)
- Plasma storage (6ml)
- DNA paxgene will be collected (8.5ml)
- RNA paxgene will be collected (2.5ml)
- Peripheral blood mononuclear cell (50 ml)

At all study visit including the first study visit the following **clinical laboratory** tests will be done:

- Hepatitis C viral load

After the first 2 weeks while on maraviroc (day 14/week 2 for the immediate start group; and day 70/week 10 for the delayed start group) the following **safety assessment** will be done:

- HIV VL, CBC with differential, and CD4 count (24.5 ml)
- Patient reports of adverse effects

Every week while taking maraviroc, and once every 4 weeks prior to starting, and after completing maraviroc, the following **clinical assessments** will be done:

- Adverse event monitoring (patient reports of adverse effects)
- Medication review

At study visits every 4 weeks including the first study visit the following blood specimens may be collected for **research laboratory** storage and tests (total 68.5 ml research, or about 4.6 tablespoons):

- RNA paxgene (2.5ml)
- Peripheral blood mononuclear cell (50 ml)
- Serum storage (10 ml)
- Plasma storage (6ml)

Outside Tests: Tissue may be requested from liver biopsies done for clinical purposes; imaging, FibroScan or other liver evaluation results may also be requested from outside providers with subject consent.

6.3 HCV and HIV Virologic Studies

We will study the viral and host immunity to HCV and HIV in all patients. The results will be used to characterize each individual with regards to immune status and chronicity of disease.

A] Full length HCV genome sequencing will be performed on plasma using the protocol as described and compared for variability of sequences.

B] Genome-wide transcriptional profiling Sequencing will be performed using RNAseq approach. This will provide the most comprehensive coverage of the genome, including empirically supported and predicted transcribed sequences,

enabling the discovery of previously unidentified novel events. We will analyze array data from samples from whole blood pax genes and will design a low-density PCR array of 20-30 genes of most interest that are highly representative of the analysis group for validation.

We will screen patient samples for miRNA panel that comprises of over 400 known, well-characterized miRNAs. The TaqMan Array Human MicroRNA Panel (Applied Biosystems, Inc.) is a fixed-set microfluidic card that simplifies the profiling of 400plus human miRNAs. After extracting RNA and making cDNA we will use the Multiplex RT and TaqMan MicroRNA Reverse Transcription Kit loaded on the micro-fluidic card, and run on the Applied Biosystems7900HT Fast Real-Time PCR System.

C] We will screen sera from all patients for differential expression of protein peaks that may be associated with liver fibrosis and HCC with the aid of a high-throughput approach using multiplex cytokine arrays, which has the capability of detecting several different cytokines and other biologically relevant proteins.

D] We will perform detailed phenotypic and functional evaluation of immune cell types in the periphery and liver (as available). This will help us in determining the nature of immune responses in patients who are chronically infected. Determination of specific immune defects in these individuals are important milestones in deciding future therapeutics. Exhaustion and activation markers on T, B and NK cells will be quantified. Specific immune responses against pooled HBV and HCV peptides will be performed using an ELISPOT assay and flow cytometry as previously described.

7 Potential Risks and Benefits

7.1 Potential Risks

The potential risks includes risks of phlebotomy which include: pain, bruising, fainting and very rarely, infection. These risks will be minimized by having trained staff perform the procedure.

There is potential for loss of confidentiality, which will be minimized by providing privacy during study visits. In addition, all laboratory specimens, and research records will be coded by a number to maintain subject confidentiality. All paper records will be kept locked with limited access. Electronic data will be password protected and will not include participant names or contact details.

Risks with Use of Maraviroc (MVC, Selzentry™)

Common side effects reported with maraviroc that may or may not be causally related include: cough, fever, colds/upper respiratory tract infections, rash,

muscle and joint aches, stomach pain, diarrhea, edema, sleeping problems, and dizziness.^{25,26}

Serious side effects may include serious skin rash and allergic reactions, and elevations in liver function tests. People who are co-infected with hepatitis B or C might be at higher risk of having liver problems, although data from trials showed similar rates of liver function test abnormalities in patients on maraviroc compared to placebo groups.

Postural hypotension was reported in patients taking higher doses (than currently approved) of maraviroc in clinical studies.²⁵

Post-marketing experience has reported skin and subcutaneous tissue disorders including Stevens-Johnson syndrome (a severe and sometimes fatal form of skin rash).

Maraviroc contains soya lecithin. Therefore if you have a medical history of allergy to soya or peanuts, you may develop an allergy reaction to maraviroc.

7.2 Potential Benefits

Participants will derive no direct clinical benefit from participation in this protocol. It is hoped that this research will be of benefit to society by aiding the understanding of immunological and virological aspects associated with the disease.

8 Stored Samples and Future Research

Future use of the specimens will be based on the scientific merit of the investigation and would be decided by the Principal Investigator. They would be related to the study of HCV and/or HIV. Other investigators may wish to study these samples and/or data. In that case, IRB approval must be sought prior to any sharing of samples and/or data. Any clinical information shared about the sample would similarly require prior IRB approval. If approved, and once a Material Transfer Agreement (MTA) has been established, the study team may send de-identified samples to the collaborators. Investigators will use stored samples only for research.

- **Intended Use:** Some tissue and blood samples may be stored for future analysis in this research study. These samples will be stored by the IHV researchers and may be used in future research to learn more about HCV and HIV, the immune system and/or other related medical conditions. The blood and tissue will be used over time to gain a better understanding of the pathogenesis of HCV and HIV, and especially the degree of liver disease progression. Genetic testing will be performed. Different analytical and laboratory methods will be employed including but not limited to: PCR, ELISA, ELISPOT and immunohistochemistry; RNA/DNA,

cytokine and antibody quantitation; viral particle detection and identification of genetic markers. The consent will include language for specimen storage.

- **Storage:** Samples will be kept in secure facilities with limited access. Samples and data will be stored using a unique identifier. Only investigators and study staff will have access to the samples and data.
- **Tracking:** Extra blood and tissue samples will be stored using a unique identifier that only the study team can trace back to the participants. These stored samples as well as a linkage file will be maintained in a database that will be managed by the Investigators and/or Study Coordinators and will be maintained on the IHV server. This database will also be stored on the password-protected computer of the Lead-Investigator/Study Coordinator in an encrypted and/or password-coded file.
- **Disposition at the Completion of the Protocol:** At the completion of the protocol (termination), samples and data will either be destroyed, or after IRB approval, transferred to another existing protocol. Final disposition of any samples cannot be done without written permission from the PI.
- **Reporting the Loss or Destruction of Samples/Specimens/Data to the IRB:**
 - Any loss or unanticipated destruction of samples or data resulting in a violation that compromises the scientific integrity of the data collected for the study will be reported to the IRB.
 - Participants may request at any point not to have their samples stored. In this case, the Principal Investigator will destroy all known remaining samples and report what was done to both the participant and to the IRB. This decision will not affect the subject's participation in any other protocols.

Generally, the results from the research stored samples will not be given to the participant's primary care provider or appear in the medical record. This is because the test results, unlike routine medical testing, may be experimental or preliminary. The relevance of these tests to direct patient care may be unknown. At the participant's request, the results of any research tests will be discussed with the primary care physician by the Investigators.

9 Assessment of Safety & Monitoring

As this is an observational study with intervention limited to blood collection, safety issues are not expected. Only those reportable Adverse Events (AEs) related to the research procedures will be reported. The PI will review the safety data and report any unexpected events to the IRB along with annual continuing review.

9.2 Definitions

Adverse Event: Any untoward medical occurrence in a human subject, including any abnormal sign, symptom, or disease, temporally associated with the subject's participation in research, whether or not considered related to the subject's participation in the research.

Protocol Deviation: Any change, divergence, or departure from the IRB approved study procedures in a research protocol. Protocol deviations are designated as serious or non-serious and further characterized as:

- Those that occur because a member of the research team deviates from the protocol.
- Those that are identified before they occur, but cannot be prevented.
- Those that are discovered after they occur

9.2.1 Reporting Protocol Deviations, AEs and Deaths

Anticipated deviations in the conduct of the protocol will not be reported to the IRB unless they occur at a rate greater than anticipated by the study team. Expected adverse events will not be reported to the IRB unless they occur at a rate greater than that known to occur in those having phlebotomy procedures normally. If the rate of these events exceeds the rate expected by the study team, the events will be classified and reported. Deaths related to the natural history of hepatitis or co-infection will be reported at the time of continuing review.

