6.1 Clinical Evaluations	17
6.2 Laboratory Evaluations.....	17
6.3 HCV and HIV Virologic Studies	18
7 Potential Risks and Benefits	19
7.1 Potential Risks.....	19
7.2 Potential Benefits.....	20

TABLE OF CONTENTS

8	Stored Samples and Future Research.....	20
9	Assessment of Safety & Monitoring	21
9.1	Recording/Documentation	22
9.2	Definitions.....	22
9.2.1	Reporting Protocol Deviations, AEs and Deaths	22
9.2.2	Annual Reporting to the IRB.....	22
9.3	Type and Duration of the Follow-up of Subjects after Adverse Events.....	23
9.4	Withdrawal of a Subject.....	23
9.5	Return of Withdrawn/Removed Subjects	23
10	Remuneration Plan for Subjects.....	24
11	Statistical Considerations	24
11.1	Sample size	24
11.2	Description of the Analyses	24
12	Ethics/Protection of Human Subjects	24
12.1	Informed Consent Process	24
12.1.1	Illiteracy and Consenting.....	25
12.2	Subject Confidentiality	25
	Appendix A: Scientific References	25
	Appendix B: Schedule of Procedures/Evaluations	28

List of Abbreviations

AE	Adverse Event/Adverse Experience
Coinfection	Identifier for those with both HIV and hepatitis B or C
DAA	Directly Acting Antiviral
ART	Highly Active Anti-retroviral Therapy
HBV	Hepatitis B Infection
HCV	Hepatitis C Infection
HIPAA	Health Insurance Portability and Accountability Act
MAVERIC	Study short name
IHV	Institute of Human Virology
IRB	Institutional Review Board
N	Number (typically refers to number of subjects/sample size)
PI	Principal Investigator
RT-PCR	Reverse Transcriptase Polymerase Chain Reaction
SAE	Serious Adverse Event/Serious Adverse Experience
SVR	Sustained Virologic Response 12 weeks following therapy
VL	Viral Load
WHO	World Health Organization

Protocol Summary

- Full Title:** **A Pilot Study to Evaluate Anti-HCV Effect of Maraviroc in HIV/HCV Co-infected Patients**
- Short Title:** MAVERIC
- Conducted by:** Institute of Human Virology, University of Maryland
- Principal Investigator:** [name]
- Sample Size:** N= 10
- Accrual Ceiling:** 15
- Study Population:** Adults infected with viral hepatitis C and being treated for HIV infection
- Study Design:** Single-site, longitudinal, open-label, interventional pilot study for evaluation of the effectiveness of Maraviroc on HCV viral levels in patients with HCV and HIV undergoing antiretroviral therapy. Participants will be seen at a IHV Clinic, Baltimore MD 21201.
- Study Duration:** *Start Date:* August 1, 2016
End Date: August 1, 2017.

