9.2.2 Annual Reporting to the IRB

The following items will be reported to the University of Maryland IRB in summary at the time of Continuing Review:

- Serious adverse events or deaths that are not related to the research
- All adverse events associated with research including expected AEs Protocol deviations. This includes AEs related to phlebotomy within 48 hours of procedure.
- Serious, continuing, and minor non-compliance
- Any trends or events which in the opinion of the investigator should be reported

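### Section 9.2.1 ties IRB reporting of expected adverse events to a phlebotomy rate and then to an unquantified team-expected rate, while 9.2.2 and 9.3 set no rate condition; neither trigger suits maraviroc effects in 10 to 15 participants

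*Combined protocol and SAP*

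**What the plan says.** Section 9.2.1 of the combined protocol and SAP gives two rules for expected adverse events. The first is "Expected adverse events will not be reported to the IRB unless they occur at a rate greater than that known to occur in those having" ordinary phlebotomy. The second, in the next sentence, uses a different comparator: "If the rate of these events exceeds the rate expected by the study team, the events will be classified and reported". No figure is given for either rate, and the denominator (participants, visits or blood draws) is not stated. The same section sends deaths from the natural history of hepatitis or co-infection to continuing review.

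Section 9.2.2 lists what goes to the IRB in summary at continuing review. One item is "All adverse events associated with research including expected AEs", with no rate condition. Another is "Serious adverse events or deaths that are not related to the research", which can be filled only if seriousness and relation have been judged. Section 9.3 follows serious and non-serious events to resolution or stabilisation and provides for annual reporting, again with no rate condition.

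Section 7.1 gives phlebotomy risks and drug risks separately. The drug list opens "Common side effects reported with maraviroc that may or may not be causally related include" and names cough, fever, rash, diarrhea, edema and dizziness among others, without rates. The opening of Section 9 nevertheless describes the trial as observational, with blood draws as the only intervention. Section 2.2 makes the safety and tolerability of adding maraviroc a secondary objective. Sections 6.1 and 6.2 collect patient-reported adverse effects weekly on drug and every four weeks off drug.

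**The concern.** Someone holding a single expected event, say a rash in week 2 of maraviroc, cannot tell from the protocol what to do with it. The phlebotomy rule, the team-expected rule and the continuing-review rule may give different answers, and the first two cannot be applied at all without figures that the protocol does not supply.

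The phlebotomy comparator is also the wrong kind of benchmark. How often people feel unwell after a blood draw says nothing about how often rash, cough or diarrhea should be expected on a CCR5 antagonist. The wording fits a blood-collection study, which is how Section 9 describes this trial, although every participant is to receive four weeks of study drug.

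Finally, the sentence quoted from 9.2.1 is the only place in the supplied text that expressly provides for classifying adverse events, and it does so only for events above a rate. At stake are consistent reporting to the IRB and a clear basis for judging seriousness, severity and relation in an open-label trial.

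**Working it through.** **Text check.** For an expected event that is associated with the research:

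- 9.2.1, first rule: report if the rate exceeds that of ordinary phlebotomy (no figure).
- 9.2.1, second rule: classify and report if the rate exceeds what the team expects (no figure).
- 9.2.2: report at continuing review, no rate condition.
- 9.3: annual reporting, no rate condition. It is unclear whether this covers all followed events or only those followed after a participant leaves the study.

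**How a rate trigger behaves at this size.** The plan has no figure to reproduce, because it states no expected rate.

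Inputs from the Protocol Summary: planned n=10, accrual ceiling 15. Assumed: expected rate p0, varied from 5% to 30%, with rate taken as the proportion of participants affected.

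The trigger needs the smallest count k with k/n above p0, that is k = floor(n × p0) + 1. The probability of staying below it is P(X ≤ k−1), with X binomial(n, true rate).

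Worked case, p0 = 10%, so k = 2 at both sample sizes:

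- n=10, true rate 20%: 0.8^10 + 10 × 0.2 × 0.8^9 = 0.107 + 0.268 = 0.376.
- n=15, true rate 20%: 0.8^15 + 15 × 0.2 × 0.8^14 = 0.035 + 0.132 = 0.167.
- n=10, true rate 30%: 0.028 + 0.121 = 0.149.
- n=15, true rate 30%: 0.005 + 0.031 = 0.035.

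In each sum the first term is the chance that nobody is affected. The second is the chance that one participant is affected and the trigger stays silent; only that part is due to the rule.

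The trigger also fires when nothing is amiss. With a true rate equal to the expected 10%, P(X ≥ 2) = 1 − 0.9^10 − 10 × 0.1 × 0.9^9 = 1 − 0.349 − 0.387 = 0.264 at n=10, and 0.451 at n=15.

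Range over the assumption:

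| n | Expected rate (assumed) | Affected needed | P(trigger) if true rate = expected | P(no trigger) if true rate = double |
|---|---|---|---|---|
| 10 | 5% | 1 | 0.401 | 0.349 |
| 10 | 10% | 2 | 0.264 | 0.376 |
| 10 | 20% | 3 | 0.322 | 0.167 |
| 10 | 30% | 4 | 0.350 | 0.055 |
| 15 | 5% | 1 | 0.537 | 0.206 |
| 15 | 10% | 2 | 0.451 | 0.167 |
| 15 | 20% | 4 | 0.352 | 0.091 |
| 15 | 30% | 5 | 0.485 | 0.009 |

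In the 5% rows one affected participant already exceeds the rate, so no trigger simply means no event. At n=10 this holds for any expected rate below 10%. At n=15 it holds below 1/15 = 6.7%.

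For scale, one affected participant in 10 is an observed 10% with an exact (Clopper-Pearson) 95% interval of 0.3% to 44.5%.

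**The case against.** The strongest case on the other side has four parts.

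*The sections may describe two tiers.* 9.2.2 is about the annual summary, and 9.2.1 itself routes natural-history deaths to continuing review, which suggests that its other rules concern earlier reporting. An expected event below the rate would then miss prompt reporting but appear in the annual summary. A reader might infer a flat contradiction; the documents do not force that reading. What remains is that 9.2.1 carries no timing qualifier, and that its two comparators still differ from each other.

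*Nothing says that events below the rate stay unclassified.* A reader might infer that classification is withheld. Section 9.2.1 does not say this, and 9.2.2 and 9.3 presuppose that seriousness has been judged, as 9.2.2 does for relation. This objection stands. The supportable point is narrower: no unconditional rule for classification is written down.

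*IRB reporting is not the trial's safety data.* A reader might infer that the safety objective cannot be met. Sections 6.1, 6.2 and 9.1 have adverse events elicited and recorded whatever the IRB threshold, the secondary endpoint is patient-reported events, and dated visits allow on-drug and off-drug status to be derived. This stands too. The principal investigator's review of safety data and the 9.2.2 item on trends are further backstops.

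*The rule may not reach maraviroc effects at all.* If expected means expected from phlebotomy, a rash on drug falls outside 9.2.1. That is possible given how Section 9 opens, but it would leave drug effects with no express classification rule, so the gap moves rather than closes. Under the wider reading, an effect not normally linked to blood draws might exceed the phlebotomy rate at the first event. The hold-back would then arise mainly through the team-expected rate.

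**Conclusion.** The point holds as a defect in the reporting rule. Section 9.2.1 uses two unquantified comparators. One of them is unsuitable for the drug effects in 7.1, and its relation to 9.2.2 and 9.3 is left for the reader to guess. The only express provision for classifying adverse events hangs on the same condition.

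The numerical size depends on an expected rate that the protocol does not give. At an assumed 10%, a doubled rate escapes the trigger with probability 0.38 at n=10 and 0.17 at n=15. At higher assumed rates a doubling is caught more often, and below 10% one affected participant in 10 is enough. It would therefore be too strong to say that a rate trigger can never work here: at an assumed 10% it catches a doubling with probability 0.62 at n=10 and 0.83 at n=15. It is unreliable, in both directions, for effects expected at around 10% or somewhat above.

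The consequence is inconsistent and possibly delayed reporting, not loss of the safety objective.

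**What to change.** - In 9.2.1, remove the rate condition and the phlebotomy comparator for events possibly related to maraviroc.
- State that seriousness, severity and relation to maraviroc are assessed for every adverse event when it is recorded, independently of any IRB reporting threshold.
- Reconcile 9.2.1 with 9.2.2 and 9.3 so that one rule says which expected events go to the IRB promptly and which go in the annual summary.
- Bring the opening of Section 9 into line with a trial that administers a study drug.

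The cost is a few sentences in Section 9 and standard classification fields on the adverse-event form, for 10 to 15 participants. It adds no visits or samples and does not alter the analysis of the primary endpoint.
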